## 4.2 Enrollment

Approximately 90 subjects will be randomized into Stage 1 and 60 into Stage 2. Subjects will be randomized from 2 to 5 days prior to the Day 1 visit. Randomization should be done after the subject has completed the screening assessments and after it has been determined that the subject meets all the inclusion and exclusion criteria.

Assess eligibility status for inclusion into the trial based on protocol inclusion/exclusion criteria, including results from screening lab assessments.

#### 4.3 Day 1 Visit

Subjects should fast for at least 8 hours (overnight) prior to this visit. The Day 1 visit assessments will serve as the baseline assessments, unless otherwise specified.

- 1. The medical history should be reviewed and updated to include any changes occurring since the screening visit.
- 2. Assessment of eligibility
- 3. Vital signs (temperature/pulse/supine blood pressure)
- 4. Physical examination (including weight)
- 5. Hematology
- 6. Serum chemistry
- 7. Urinalysis
- 8. Serum hormones
- 9. Bone turnover markers
- 10. Record the usage of any concomitant medications and ongoing treatments
- 11. Adverse events (ongoing on Day 1)
- 12. Caprini VTE Risk Assessment
- 13. Blood samples for pharmacokinetic (PK) assessment
- 14. Assess hot flashes
- 15. Dispense study drug
- 16. First dose- instruct the subject to take his capsule at the same time each day

## 4.4 Day 14 Visit

The following assessments will be conducted on Day 14 ( $\pm$ 3 days):

- 1. Vital Signs (temperature/pulse/supine blood pressure)
- 2. Serum chemistry
- 3. Record the usage of any concomitant medications and treatments
- 4. Adverse events

## 4.5 Day 30 and Day 60 Visits

Subjects should fast for at least 8 hours (overnight) prior to these visits. The following assessments will be conducted on Day 30 ( $\pm$  7 days) and Day 60 ( $\pm$  7 days):

- 1. Vital Signs (temperature/pulse/supine blood pressure)
- 2. Serum chemistry
- 3. Hematology
- 4. Serum hormones
- 5. Blood samples for PK assessment
- 6. Record the usage of any concomitant medications and treatments
- 7. Assess hot flashes
- 8. Caprini Venothromboembolism Risk Assessment
  - a. If there is an increase in risk from baseline (Day 1) in this assessment, appropriate preventative actions should be taken. The subject should be consulted about the risk for VTE and actions that would increase their risk further such as long periods of inactivity and surgery. Prophylactic anticoagulation therapy should be considered.
  - b. If a subject has a prolonged PTT-LA or is deficient for Protein C and/or Protein S, but remains eligible for participation in the study, prophylactic anticoagulation therapy should be considered.
  - c. For Protein C or Protein S deficiency, consideration should be given to dietary changes to increase Vitamin K intake.
- 9. Adverse events
- 10. Collect capsule bottles and perform capsule accountability/compliance assessment
- 11. Dispense study drug

## 4.6 Day 84 Visit (End of Study Visit)

Subjects should fast for at least 8 hours (overnight) prior to this visit. The following assessments will be conducted on Day 84 ( $\pm$  7 days):

- 1. Vital Signs (temperature/pulse/supine blood pressure)
- 2. Physical examination (including weight)
- 3. Serum chemistry (Appendix 9.1) (central laboratory)
- 4. Hematology (Appendix 9.1) (central laboratory)
- 5. Serum hormones (Appendix 9.1) (central laboratory)
- 6. Blood samples for pharmacokinetic assessment
- 7. Bone turnover markers

- 8. Record the usage of any concomitant medications and treatments
- 9. Adverse events
- 10. Assess hot flashes (see Appendix 9.3)
- 11. Caprini Venothromboembolism Risk Assessment (Appendix D)
  - It is important to note that it is expected that the patient population included in this study will have some risk of VTE due to age, presence of a malignancy, and BMI. The purpose of this assessment is a change in risk from baseline. Also, while the questionnaire is designed for the patient to complete, in this study, the Caprini VTE risk assessment should be filled out by study personnel with information from the patient and patient's chart.

If there is an increase in risk from baseline (Day 1) in this assessment, appropriate preventative actions should be taken. The subject should be consulted about the risk for VTE and actions that would increase their risk further such as long periods of inactivity and surgery. Prophylactic anticoagulation therapy should be considered.

12. Collect capsule bottles and perform capsule accountability/compliance assessment

#### 4.7 Follow-up Visit

The following assessments will be performed 30 days ( $\pm$  7 days) after the End of Study visit (Day 84):

- 1. Vital Signs (temperature/pulse/supine blood pressure)
- 2. Physical examination (including height and weight)
- 3. Adverse events

#### 4.8 eDiary Assessment

Subjects will be provided with an Electronic Diary (eDiary) at the Screening Visit to collect data for hot flashes during screening. If enrolled, they will continue to use the eDiary to collect hot flash information for each hot flash through Day 84/Early Termination. All subjects should be instructed to return the eDiary to the study site. Subjects must be educated to record the hot flash assessments in the eDiary in real time.

The table in Appendix 9.1 outlines the timing of assessments to be recorded throughout the study in the eDiary. Appendix 9.3 further elaborates on the hot flash assessment and provides a list of the three severity levels of hot flashes along with a description of the symptoms associated with each level.

## 5. ANALYSIS POPULATIONS

The subjects will be over the age of 18 and will have moderate to severe hot flashes, defined as a minimum of 4 moderate to severe hot flashes per day or 12 per week at baseline. The 4populations are as follows:

Intent-to-Treat (ITT) population:	All enrolled subjects who have taken at least 1 dose of study drug.
Efficacy Evaluable (EE) population:	All subjects in the ITT population who have analyzable baseline data and 12 weeks of hot flash data. Subjects must also be at least 80% compliant with taking study drug with no major protocol deviations, including no major inclusion/exclusion deviations.

Efficacy Evaluable (EEIA) population for IA:	All subjects in the ITT population who have analyzable baseline data and 6 weeks of hot flash data. Subjects must also be at least 80% compliant with taking study drug with no major protocol deviations, including no major inclusion/exclusion deviations.
Safety population:	All subjects who receive at least 1 dose of study drug. The safety analyses will be conducted on this population. This population is the same as the ITT population.

## 6. STATISTICAL METHODOLOGY

## 6.1 Statistical and Analytical Issues

## 6.1.1 Statistical Methods

For quantitative variables, descriptive statistics will include the number of subjects (n), mean, standard deviation (SD), median, minimum and maximum. Categorical variables will be summarized using the number (n) and percentage (%) of subjects for each category. Unless otherwise specified, the denominator for all percentages will be the number of subjects in the respective treatment group who have data for the respective time point in the applied analysis population. Percentage change from baseline will be calculated using the non-missing (see section 6.1.2) data of both baseline and the respective post-baseline value.

The primary efficacy analyses will only include efficacy data that were captured in the eDiary for hot flashes which were treated with study drug (VERU-944 or placebo). All baseline measurements for efficacy will be collected prior to dosing in the treatment period. By default the frequency and severity of hot flashes at baseline will be determined from the second week of the first two weeks of hot flash eDiary that were recorded; If a patient qualified for the study entry by number of hot flashes during the second week of screening, then data from that week will be used as their baseline. However, if a patient did not qualify for study entry based on the number of hot flashes during that second week then data from the screening week that was used to qualify the patient will be used as their baseline instead. Percentage change from baseline is defined as the post-baseline value of interest minus the baseline value then divided by the baseline value and finally converted to a percentage by multiplying by 100.

A 1-sided alpha level equal to 0.10 will be used to determine statistical significance for the primary and secondary efficacy objectives related to hot flash frequency and severity.

For the treatment period, baseline for the safety assessments will be defined as the Day 1 assessment, or if missing, the last assessment prior to dosing.

All data processing, summarization, and analyses will be performed using SAS® Version 9.4 or higher. Specifications for table, graph, and data listing formats can be found in the tables, listings, and figures (TLF) specifications. Adverse events will be classified using the Medical Dictionary for Regulatory Activities (MedDRA) dictionary, Version 18.1 or higher. All concomitant medications will be coded using the World Health Organization Drug Dictionary Enhanced (WHODDE), version Sep2015 or later.

#### 6.1.2 Handling of Dropouts and Missing Data

Subjects must have entered hot flash data (frequency and severity) for 4 or more days in a given week for their data to be considered non-missing. No other imputation procedures will be used to impute missing data. If a subject enters that there are no hot flashes to report on a given day, then this will be considered a data point equal to zero. If a subject does not report any hot flash information across consecutive days,

the data management team will be alerted to query the situation. From a data perspective, if a subject fails to report hot flash information on a given day, then that day will be recorded as missing.

For determining whether adverse events (AEs) are treatment-emergent when the start date of the AE is a partial date, refer to Section 6.4.1.

For determining whether a medication is a prior medication or concomitant medication, refer to Section 6.2.5.

## 6.1.3 Pooling of Investigative Sites

All site data will be combined and analyzed together.

## 6.1.4 Determination of Sample Size

The proposed trial sample size, n=30 per arm, total N=90 in Stage 1, is based on at least a 40% reduction in the mean weekly frequency of hot flashes in a treated arm versus placebo from baseline to Week 4 (Day 28) [the planned primary endpoint at the time of the original study design]. Other assumptions to derive the sample size include a 1-sided  $\alpha$ =0.10, a  $\beta$ =0.10 (i.e., power=0.9), and equal variances in the placebo and active arms. The variance was set to equal the mean of the active arm. The same assumptions hold for Stage 2, with a proposed sample size of n=30 per arm, N=60 in Stage 2.

Note, all subjects in screening at the time the 90th subject is randomized into Stage 1 will qualify to be randomized into Stage 1 up to a maximum of 120 subjects (40 per arm). In Stage 2, all subjects in screening at the time the  $60^{th}$  subject is randomized into Stage 2 will qualify to be randomized into the study up to a maximum of 80 subjects (40 per arm). The total enrollment, if both stages are completed, will be a minimum of N=150.

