### **6.2 Selection Criteria**

#### **6.2.1 Inclusion Criteria**

Subjects accepted for this study must:

1. Be over 18 years of age
2. Be able to communicate effectively with the study personnel
3. Have histologically confirmed prostate cancer
4. Have been treated with an LHRH agonist or LHRH antagonist for at least the 2 months prior to randomization
5. Be continued on an LHRH agonist or LHRH antagonist throughout this study (must be continuous therapy)
6. Have experienced hot flashes for at least one month prior to study entry
7. Have moderate or severe vasomotor symptoms (hot flashes) (defined as a minimum of 4 moderate to severe hot flashes per day or 12 per week at baseline)
8. ECOG performance status of 0 to 2
9. Be willing to use electronic data capture for the relevant medical events
  - Must be at least 80% compliant during the screening period (for the 14 contiguous day hot flash assessment that is required during screening)
10. Subjects must agree to use acceptable methods of contraception
  - If their female partners are pregnant or lactating, acceptable methods of contraception from the time of the first administration of study medication until 6 months following administration of the last dose of study medication must be used. Acceptable methods are: Condom used with spermicidal foam/gel/film/cream/suppository. If the subject has undergone surgical sterilization (vasectomy with documentation of azospermia), a condom with spermicidal foam/gel/film/cream/suppository should be used
  - If the male subject's partner could become pregnant, use acceptable methods of contraception from the time of the first administration of study medication until 6 months following administration of the last dose of study medication. Acceptable methods of contraception are as follows: Condom with spermicidal

foam/gel/film/cream/suppository [i.e., barrier method of contraception], surgical sterilization (vasectomy with documentation of azospermia) and a barrier method {condom used with spermicidal foam/gel/film/cream/suppository}, the female partner uses oral contraceptives (combination estrogen/progesterone pills), injectable progesterone or subdermal implants and a barrier method (condom used with spermicidal foam/gel/film/cream/suppository)

- If the female partner has undergone documented tubal ligation (female sterilization), a barrier method (condom used with spermicidal foam/gel/film/cream/suppository) should also be used

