## **9.0 STATISTICAL ANALYSIS**

### **9.1 Sample Size Calculation**

The proposed trial sample size,  $n=30$  per arm, total  $N=90$  in Stage 1, is based on the mean change in hot flash frequency from baseline to Week 4 (Day 28) (the planned primary endpoint at the time of the original study design). Other assumptions include: one-sided  $\alpha=0.10$ ;  $\beta=0.10$  (i.e., power=0.9), equal variances, the variance is equal to the mean of the active arm, and a frequency in at least one treated arm that is 40% less than that of the placebo arm on Week 4 (Day 28). The same assumptions hold for Stage 2 as well with proposed trial sample size of  $n=30$  per arm,  $N=60$  in Stage 2. Total enrollment if both stages are completed will be approximately  $N=150$ .

All patients in screening at the time that the 90th patient is randomized into Stage 1 of the study that qualify for the study will be randomized into the study up to a maximum of 120 patients (40 per arm). In Stage 2, all patients in screening at the time the 60th patient is randomized into Stage 2 of the study that qualify for the study will be randomized into the study up to a maximum of 80 patients (40 per arm).

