## Adjustment for Multiple Comparisons

The Hochberg procedure will be applied to control for multiplicity for each of the primary and secondary hot flash related endpoints. Each endpoint will have 4 analyses associated with them to account for the two active dose arms (10 mg and 50 mg) each compared to baseline by two methods each (MMRM test for slope and MMRM test for change from baseline at the specified week). These may be referred to as sets of analyses. Hochberg is a step-up procedure based on univariate p-values. This procedure begins

with the least significant p-value and then examines the other p-values in sequential order, making alpha level adjustments along the way, until a significant p-value is observed. Once achieved, all following lower p-values in the sequence would be considered significant. For example, if one has 4 hypotheses the following will be performed:

- Step 1: Order the p-values from largest (least significant) to smallest (most significant)
- Step 2: Using the pre-specified overall alpha level,  $\alpha_0=0.10$ , one-sided, compare the largest p-value, P1, to the overall alpha level. If P1<0.10 then all (null) hypotheses are rejected; otherwise go to step 3.
- Step 3: Compare the second largest p-value, P2, to  $\alpha_1$ =0.10/2=0.05. If P2<0.05 then this and all further hypotheses are rejected; otherwise repeat for the third, P3, and fourth, P4, largest p-values compared with  $\alpha_2$ =0.10/3=0.033 and  $\alpha_3$ =0.10/4=0.025 as necessary to either reject all remaining hypotheses or conclude no significant difference exists.

For this study, during Stage 1, Hochberg's procedure will rank the p-values from highest to lowest for each statistical test within each set of analyses: 10 mg versus placebo slope difference (through Week 6), 50 mg versus placebo slope difference (through Week 6), 10 mg versus placebo mean difference at week 6, 50 mg versus placebo mean difference at Week 6. Adjustment for the single comparison of 100 mg versus placebo in Stage 2 will be necessary only for the two MMRM modes, means and slopes.

Overall, for the multiple tests of primary and secondary endpoint analyses alpha control will be achieved by a gate-keeping method such that the endpoints are ordered and the preceding endpoint must be shown to be significant in order for endpoints down the list to be eligible for significance.

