## 6.3.1.1 Primary Efficacy Endpoint Analysis (Hot Flash Frequency at Week 6)

STAGE 1:

The primary frequency efficacy endpoint is percentage change in frequency of moderate and severe hot flashes (vasomotor symptoms) from the baseline week to Week 6 (Day 42). The statistical tests for significant differences with regards to the percentage change between placebo and each of the active arms, 10 mg 50mg, and perhaps 100 mg comprise the main tests of interest.

The SAS code for performing the MMRM analyses to test for a significant difference in the MEAN percentage change in frequency of moderate to severe hot flashes between each of the dose arms and placebo evaluated at Week 6 (primary analysis week) is shown below. Note that this analysis will generate two of the four tests that are part of the primary analysis to which the Hochberg procedure will apply.

PROC MIXED DATA= XXX; CLASS subjid tx week; MODEL cfb = tx week\_2 tx\*week\_2; REPEATED week / type=AR(1) sub=subjid(tx); LSESTIMATE tx\*week '10MG VS Placebo at Week 6' [1, 10 6] [-1, P 6]; LSESTIMATE tx\*week '50MG VS Placebo at Week 6' [1, 50 6] [-1, P 6]; WHERE week le 6; RUN;

The variables used in the above model will be defined as follows: tx=treatment; week (1, 2... 6); cbf=change from baseline value, week\_2=week (week will be treated as a categorical variable in the class statement and week\_2 will be treated as a continuous variable in the model... effectively the values of these variables will be an exact match). By creating week\_2 in a preceding data step, this allows for LESTIMATES to be computed at a specific WEEK (treated as categorical in the CLASS statement) but allows week to be treated as a continuous variable, WEEK\_2 in the model.

This model will be run 3 separate times using 3 separate covariance structures to determine best fit. The same model will be run, with the following specified change on the REPEATED line: (1) type=AR(1); (2) type=CS; and (3) type=UN. If a model does not converge, then disregard that model. If more than 1 model remains, then refer to the Akaike's Information Criteria (AIC) score to determine model fit. The best fit model will be chosen as having the AIC value closest to zero. The model type chosen will be referenced in the footnote for each model output.

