## STAGE 2:

The analyses conducted in Stage 2 will be the exact same as in Stage 1, except the 10 mg and 50 mg dose of study drug will be replaced with a 100 mg dose of study drug. A separate and distinct placebo group will be used for Stage 2. The Hochberg procedure will have to address only two multiple comparisons, i.e., the MMRM slope models and the MMRM means models as there is now only one dose level comparison to placebo. The two alpha levels that may be needed to assess significance will be only  $\alpha_0=0.10$  and possibly  $\alpha_1=0.05$ . Here is the appropriate code for the LSESTIMATE statement.

LSESTIMATE tx\*week '100MG VS Placebo at Week 6' [1,100 6] [-1, P 6];

Also, as a reminder, the SAS code shown for the primary analysis can be used in this second stage as well for its primary analysis of hot flash frequency as well as for all secondary hot flash related endpoints.

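### The weekly variance rule in SAP 6.1.4 does not reproduce 30 per arm, and on the readings that do, 0.90 is the unadjusted power of one Week 4 comparison

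*SAP*

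**What the plan says.** SAP 6.1.4 sizes Stage 1 at 30 per arm for "at least a 40% reduction in the mean weekly frequency of hot flashes in a treated arm versus placebo", at Week 4, with one-sided alpha 0.10, power 0.90 and equal variances. On the variance it says: "The variance was set to equal the mean of the active arm". Protocol 9.1 gives the same rule, "equal variances, the variance is equal to the mean of the active arm", and the same effect, "a frequency in at least one treated arm that is 40% less than that of the placebo arm", but no time unit. Both sections carry the assumptions over to Stage 2 at 30 per arm, and both disclose that Week 4 was the endpoint when the study was designed. Neither gives a placebo or active mean. The only frequency anchor is the entry criterion in Protocol 6.2.1: "a minimum of 4 moderate to severe hot flashes per day or 12 per week at baseline".

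The planned test is different. The primary endpoint is now percentage change in frequency at Week 6, analysed by MMRM. Under the multiplicity heading of SAP 6.3.1, "Each endpoint will have 4 analyses associated with them": two doses, each tested on means and on slope. Hochberg is applied at an overall one-sided 0.10, with thresholds of 0.10, 0.05, 0.033 and 0.025. For Stage 2, "The Hochberg procedure will have to address only two multiple comparisons".

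**The concern.** A variance rule tied to a mean needs that mean and its time unit before it yields a sample size. Here the unit is weekly, the mean is missing, and the obvious anchor gives a figure far from 30. A reader therefore cannot check the basis.

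The stated 0.90 also sits beside a four-test family without any mention of it. SAP 6.7 defines an effective dose in Stage 1 as a statistically significant result. It lets the sponsor forgo Stage 2 if there is one and starts Stage 2 if there is not. Readers will naturally take 0.90 as the chance that this step finds a working dose.

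**Working it through.** **Inputs.** One-sided alpha 0.10 and power 0.90, so z = 1.2816 for each; active mean = 0.6m and difference = 0.4m for placebo mean m (all from SAP 6.1.4). The value of m is not stated. The entry minimum (12 per week, or 4 per day = 28 per week) serves as an assumed anchor, with lower values also tried.

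**Formula.** n per arm = 2(1.2816 + 1.2816)² × variance / difference² = 13.139 × variance / difference².

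**Step 1: the rule as written, weekly.** Variance = 0.6m, so n = 13.139 × 0.6m / (0.4m)² = 49.27/m.

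| Placebo mean per week | n per arm |
|---|---|
| 28 | 1.8 |
| 12 | 4.1 |
| 6 | 8.2 |
| 2 | 24.6 |
| 1.64 | 30 |

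A mean of 1.64 is about 86% below the 12-per-week minimum (1 − 1.64/12).

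**Step 2: readings that return 30.**
- SD, not variance, equal to the active mean: n = 13.139 × 0.36/0.16 = 29.6 whatever the mean or time unit. By the t distribution, power is 0.892 at 29 and 0.900 at 30.
- The variance rule on a daily scale at m = 12/7 = 1.71: n = 49.27/1.714 = 28.7. By t, power is 0.899 at 29 and 0.906 at 30.

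Each is one two-arm comparison at the full 0.10.

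**Step 3: one means test at the Hochberg thresholds, n = 30.** Power = Φ(d√15 − z), where d = difference/SD. This is 0.4/0.6 = 0.667 on the SD reading and 0.676 on the daily reading.

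| One-sided level | SD = active mean | Daily, 1.71 |
|---|---|---|
| 0.10 | 0.903 | 0.909 |
| 0.05 | 0.826 | 0.835 |
| 0.033 | 0.773 | 0.784 |
| 0.025 | 0.733 | 0.745 |

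On the literal weekly rule at 12 per week, d = 4.8/√7.2 = 1.789, and power exceeds 0.999 even at 0.025.

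**Step 4: illustration under Hochberg, n = 30, Week 4 inputs.** Simulated normal statistics with one-sided p-values. The two dose comparisons have correlation 0.5 through the shared placebo arm. Means/slope correlation (0 to 0.9) and slope signal (0, 0.5 or 1 times the means signal) are assumptions, since the documents give neither.

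| Scenario | SD = active mean | Daily, 1.71 |
|---|---|---|
| One dose effective, that dose declared | 0.73–0.93 | 0.75–0.94 |
| Both effective, at least one rejection | 0.87–0.99 | 0.88–0.99 |
| Stage 2 | 0.83–0.98 | 0.83–0.98 |

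For one dose, 0.90 is passed only when the slope test is as strong as the means test and nearly uncorrelated with it. At the permitted maximum of 40 per arm (SD reading), one-dose power is 0.85–0.98 and Stage 2 power 0.91–0.99.

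**Step 5: p-values.** SAP 6.1.1 and 6.3.1 set one-sided 0.10. The slope test in SAP 6.3.1.1 takes the overall interaction p-value, which is two-sided, and then checks the direction. The means code, which supplies "two of the four tests that are part of the primary analysis to which the Hochberg procedure will apply", shows no one-sided option. If p-values enter Hochberg unhalved, one-dose power falls to 0.63–0.87 (SD) or 0.65–0.88 (daily). Stage 1 familywise error in the beneficial direction falls from 0.069–0.090 to 0.035–0.047.

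**The case against.** Several counter-arguments have force.

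- **Scope.** The calculation concerns Week 4 frequency, as both documents disclose. The SD of the Week 6 percentage change and the gain from MMRM are not given, so the Step 4 ranges are not the power of the Week 6 test. This stands, and they are offered only as an illustration.
- **Dependence on the reading.** A shortfall appears only where SD replaces variance or daily replaces weekly. On the weekly text as written, power is close to 1. This also stands. But that text does not give 30 or 0.90 either, so it cannot rescue the stated figures.
- **Both doses effective.** Here 0.90 is roughly right or conservative. This stands.
- **Convention.** Powering a Phase 2 dose-finding study on a single comparison is common, and neither document claims that 0.90 is adjusted. That supports relabelling rather than resizing.
- **Sidedness.** The stated one-sided level and the direction check show the intent. Even so, an unhalved p-value compared with a one-sided threshold is not a one-sided 0.10 test.

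Two stronger inferences should be resisted. A reader might infer that 30 per arm is too few, but the literal rule needs far fewer and two other readings need 30. A reader might also take the phrase about at least one treated arm in Protocol 9.1 as a success rule. It describes the assumed effect. The reading of success as at least one Hochberg rejection is a reasonable inference from SAP 6.7, which says only that the result must be statistically significant.

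**Conclusion.** The point holds in limited form. The weekly variance rule does not reproduce 30 at any plausible weekly mean. This rests on the entry minimum as an anchor, but the gap (about 4 against 30) is wide. The fault may lie in the description rather than the number, and the documents cannot show whether SD was meant or a daily scale was used.

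On either reading that returns 30, 0.90 is the unadjusted power of one Week 4 comparison. Under Hochberg on the same inputs it usually overstates power for one effective dose, given the assumed correlations and slope signals. No power is given for the Hochberg family or for the Week 6 percentage-change MMRM, and none can be derived from the disclosed inputs. A reader might infer inflated type I error from the p-value handling; taken literally, it is conservative and costs power instead.

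**What to change.** 1. In Protocol 9.1 and SAP 6.1.4, correct the basis so that it reproduces 30. State the placebo mean, whether the SD or the variance was set equal to the active mean, and the time unit.
2. Label 0.90 as the unadjusted power of a single comparison at one-sided 0.10 for the original Week 4 endpoint. Add Hochberg power by scenario (one dose effective, both effective, Stage 2) only if the sponsor can supply the Week 6 SD, the means/slope correlation and the slope effect.
3. In SAP 6.3.1 and its code, enter one-sided p-values in the direction of benefit into Hochberg for both tests: p/2 when the estimate favours the active arm, and 1 − p/2 otherwise.

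The cost is wording in two documents and a code setting, with no added patients. The downside is a less favourable power statement.
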